Hopelessness features prominently in suicide theories. Although hopelessness has recently been framed as primarily a predictor of SI rather than suicide attempt or death, large prospective studies demonstrate the predictive validity of baseline hopelessness for suicide death in inpatients ($n=102$)²³ and outpatients ($n=1,958$)²⁴, and a meta-analysis of longitudinal studies reports a role for baseline hopelessness as a *prospective* predictor of attempt (OR=1.95), and death (OR=2.15)²⁵. Although hopelessness is one of the best-studied constructs in suicide research, little evidence is available about dynamic changes in hopelessness and proximal suicide risk. One recent report described the use of daily surveys to evaluate links between risk factors and SI. They found that fluctuations in hopelessness successfully predicted SI severity *at the next time point* across two samples, suggesting that surges in hopelessness increase proximal suicide risk²⁶.

E2+P4 Withdrawal Causes Hopelessness. E2+P4 withdrawal paradigms increase behavioral despair in animals. While despair can be triggered by withdrawal from E2²⁷ or P4²⁸, combined E2+P4 withdrawal is most similar to the perimenstrual phase. Among other likely mechanisms of E2+P4 withdrawal on hopelessness (e.g., serotonergic), we focus on E2+P4 as regulators of GABAergic neuroactive steroids, since prevention of neuroactive steroid formation using finasteride administration (i.e., abrupt neuroactive steroid withdrawal) recapitulates E2+P4-withdrawal-induced despair in animals, even when E2 or P4 remain high²⁹. In susceptible females, withdrawal from E2+P4 provokes sadness^{27,30,31}; however, a key

limitation of this literature is that few experimental or longitudinal studies specifically examine the impact of hormone withdrawal on hopelessness.

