3.0 Objectives/Aims

Our aim is to test the **central hypothesis** is that perimenstrual E2+P4 withdrawal induces rapid withdrawal from calming GABAergic neuroactive steroids, which in turn increases hyperarousal and hopelessness, which then interact to cause proximal suicide risk (Figure 1). P4 is metabolized to GABAergic neuroactive steroids, and E2 promotes expression of enzymes that convert P4 to neuroactive steroids⁹³. Perimenstrual E2+P4 withdrawal may increase suicide risk by causing rapid withdrawal from the antidepressant⁹ and sedative^{11,10} effects of neuroactive steroids⁹⁴, as well as withdrawal from the antidepressant effects of E2⁹⁵. Our preliminary experimental work strongly suggests that perimenstrual E2+P4 withdrawal (and neuroactive steroid withdrawal) heightens proximal suicide risk via hopelessness⁶⁵ and hyperarousal^{12,66}.

Figure 1. Peri-menstrual Hormone Withdrawal and Proximal Suicide Risk

Design: Using the PI’s hormone withdrawal paradigm (K99MH109667¹²), a new sample of 90 completers female outpatients with past-month SI will complete two counterbalanced conditions: (1) natural perimenstrual E2+P4 withdrawal (placebo), and (2) perimenstrual E2+P4 stabilization. Five labs per condition will capture changes in neuroactive steroids, mRNA expression for neurosteroidogenic enzymes, physiological arousal, behavioral indices of arousal, and interview/self-report indices of proximal suicide risk, hopelessness, and hyperarousal. Our app (BiAffect) will passively track indices of arousal including psychomotor agitation (accelerometer) and reactivity (typing speed variability). Additionally, Metricwire will passively track movement using smartphone sensors. 40 healthy controls (HC) will complete five labs across one observational cycle to characterize 1) normative cycle-related variation in neuroactive steroids and mRNA expression, and 2) group-related differences (i.e., past-month SI vs HC) in trajectories of GABAAR subunit change across the cycle.

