Testing Interactive Effects of Hopelessness and Arousal on Suicide Outcomes: Interactions among hopelessness and arousal will be examined as predictors of suicide outcomes and as mediators of the experimental effect. In order to test this, we examine day-to-day interactive effects of daily person-centered hopelessness (noted above) and daily person-centered arousal indices (noted above) predicting same-daily suicide outcomes (noted above). We predict that higher-than-usual hopelessness on a given day will predict greater same-day risk on suicide outcomes, but only when arousal is *also* higher than usual for that individual.

4. Evaluating Mediation Where Appropriate. Finally, each aim indicates that **mediation** will be explored as appropriate. Only when analyses indicate significant effects of the experiment on both the suicide outcome and any mediator, as well as significant associations between the person-centered variable (or interaction variable) and the suicide outcome, we will utilize methods provided by **Bauer, Preacher, and Gil (2006)** to construct a confidence interval for the level 1 indirect effect of experimental condition (condition X phase) on the suicide outcome via the mediator.

Testing for normative cyclical change in the HC group. Aim 3 seeks to characterize how gene expression for GABA_{AR} subunits varies across pre-specified menstrual cycle phase in response to hormonal change. In N=40 HC participants, we will run multilevel growth models to predict subunit gene expression (one model per gene) from specific cycle phase. We will test all pairwise comparisons between midluteal, perimenstrual, and midfollicular phases, controlling for ALLO level, to capture high P4 and ALLO states (midluteal), P4 and ALLO withdrawal (perimenstrual), and low P4 and ALLO (midfollicular).

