- b. For laboratory visit outcomes, we will again utilize multilevel models (with 6 labs per person—3 per condition—nested within individuals; two-level models). A two-level model will predict each repeated measures lab outcome from covariates (daily pain, illness, PRN medication use) and the interaction between (1) experimental condition (a dichotomous variable coded as 0 for natural hormone withdrawal condition and 1 for hormone stabilization condition) and (2) condition phase, a categorical (contrast) variable coded as follows: *midluteal baseline visit, perimenstrual experimental visit*, and the *medication withdrawal visit*. Number of lab observations per person. For the primary contrast between the midluteal and perimenstrual experimental phases, there are 4 observations per person—2 per condition. Based on our preliminary data from the K99 trial (identical experimental manipulation), we anticipate very minimal missing laboratory data (see grant for details) but have estimated that on average each completer participant will miss .25 visits.
- c. **Hypothesized Pattern of Effects for Daily and Lab outcomes**: A significant interaction between experimental condition and condition phase is hypothesized for all twelve specified outcomes such that, in the natural withdrawal condition we expect deleterious changes from the midluteal phase to the premenstrual and menstrual phases (due to corresponding hormone withdrawal), but in the hormone stabilization condition we expect no deleterious

1 R01 MH120843-01 (PI: [name])

changes (or less severe changes) from the midluteal to the premenstrual and menstrual phases (since hormone withdrawal is prevented).

2. Testing Associations Between Mediators and Suicide Outcomes: Each aim next requires that we evaluate the day-to-day or week-to-week associations between single mediators (listed above) and suicide outcome variables on the same day or visit. This will be carried out in similar multilevel models as above, predicting each of the three primary suicide outcomes from person-centered values for each of the 9 mediators (listed above).

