3. Testing Interactive Effects of Hopelessness and Arousal on Suicide Outcomes: Interactions among hopelessness and arousal will be examined as predictors of suicide outcomes and as mediators of the experimental effect. In order to test this, we examine day-to-day interactive effects of daily person-centered hopelessness (noted above) and daily person-centered arousal indices (noted above) predicting same-daily suicide outcomes (noted above). We predict that higher-than-usual hopelessness on a given day will predict greater same-day risk on suicide outcomes, but only when arousal is *also* higher than usual for that individual.

4. Evaluating Mediation Where Appropriate. Finally, each aim indicates that **mediation** will be explored as appropriate. Only when analyses indicate significant effects of the experiment on both the suicide outcome and any mediator, as well as significant associations between the person-centered variable (or interaction variable) and the suicide outcome, we will utilize methods provided by **Bauer**, **Preacher**, **and Gil (2006)** to construct a confidence interval for the level 1 indirect effect of experimental condition (condition X phase) on the suicide outcome via the mediator.

1 R01 MH120843-01 (PI: [name]) POWER ANALYSIS.

With the funds allowed in this four-year grant, we are able to increase our proposed sample size slightly, from 80 to 85 completers, which would allow us to achieve 80% power to detect conventionally small-to-medium sized effects that, in our estimation, are clinically meaningful (i.e., $f^2 = .10$, which would mean that the interaction of condition and phase had uniquely accounted for 10% of the variance in the outcome in the perimenstrual window; Selya et al., 2012, "A Practical Guide to Calculating Cohen's f², a Measure of Local Effect Size"). We posit that if hormone withdrawal (vs. experimental stabilization) does not account for at least 10% of the variance in the outcome during this critical risky window of the menstrual cycle, then this line of research, which involves significant participant burden, is not worth pursuing further.

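### Mediators are tested against suicide outcomes only on the same day or visit, so for self-reported hopelessness and agitation a symptom that follows ideation can meet the mediation conditions as often as a true mediator

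*SAP*

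**What the plan says.** SAP Analytic Steps, step 2, evaluates single mediators against "suicide outcome variables on the same day or visit", by "predicting each of the three primary suicide outcomes from person-centered values for each of the 9 mediators". Step 3 treats the hopelessness-by-arousal interaction in the same way and predicts that "higher-than-usual hopelessness on a given day will predict greater same-day risk on suicide outcomes", provided that arousal is also raised.

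Step 4 sets two requirements before a confidence interval for the level 1 indirect effect is built. The first is that "analyses indicate significant effects of the experiment on both the suicide outcome and any mediator". The second concerns the link between mediator and outcome, and is worded "as well as significant associations between the person-centered variable (or interaction variable) and the suicide outcome". Protocol 10.0 carries the same steps.

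The hypothesis being tested, in Protocol 3.0, is a causal sequence: neuroactive steroid withdrawal, "which in turn increases hyperarousal and hopelessness, which then interact to cause proximal suicide risk". In support, Protocol 2.0 (Premise for Aim 1b) cites a daily-survey report in which "fluctuations in hopelessness successfully predicted SI severity" at the following time point.

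On measurement, Protocol 6.0 (Smartphone-Based Assessments) has hopelessness items and the Brief Agitation Measure completed once each evening as a rating of the whole day. The SAP Outcome Specification places the daily ideation score in the daily survey too.

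**The concern.** The three conditions in step 4 are an effect of the experiment on the outcome, an effect on the mediator, and an association between the two. If the labels mediator and outcome are exchanged, the list is unchanged. A symptom that merely accompanies or follows ideation can therefore meet it.

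Randomisation supports the first two links but not the third. Person-centring removes stable differences between people, not same-day reversal. The day-1 autoregressive term in the SAP is an error structure, not a lagged predictor. The multilevel path model in Protocol 3.0 is conditional and is given no time order. Because hopelessness, agitation and ideation are each rated once for the day, their order within the day cannot be recovered.

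The trial describes itself as mechanistic, so the mediation result is a main product. At stake is whether hopelessness or agitation is reported as a cause of ideation when the data fit the opposite direction equally well.

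**Working it through.** **The plan's own figure.** The documents give no operating characteristics for the mediation step. The nearest stated figure is the ideation row of the SAP power table (85 completers, ICC .64, f² = .10, one-tailed alpha .004). With 24 expected daily observations:

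- Effective N = 85 × 24 / (1 + 23 × .64) = 2040 / 15.72 = 129.8 (stated: 130).
- Noncentrality = √(.10 × 129.8) = 3.60; one-sided power at .004 = .816 (stated: .81).

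The plan's inputs reproduce, so they were carried into the simulation.

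**Simulation set-up.**

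- From the documents: 85 people; 28 days in four blocks of seven (two phases by two conditions); 15% of days missing; one-sided .004. The SAP states that alpha for power, so applying it to step 4 is an assumption.
- Effect of the experiment: .5 to 1.0 person-SD. Protocol 2.0 reports roughly 1 person-SD for ideation in the prior trial.
- Assumed, not in the documents: within-person coefficient r of .3, .5 or .7; autocorrelation .3 (.6 as a check); variation in slopes between people.
- Model: within-person regression with cluster-robust standard errors in place of the mixed model, and a 95% Monte Carlo interval for the indirect effect.
- Reverse-cause data: ideation drives same-day hopelessness, with no path back. Forward data: hopelessness drives same-day ideation.

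**Share of trials meeting all step 4 conditions with an interval excluding zero** (200 runs per cell, autocorrelation .3; reverse / forward):

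| Effect | r = .3 | r = .5 | r = .7 |
|---|---|---|---|
| .5 SD | 7.5% / 10.5% | 37% / 35.5% | 65.5% / 67% |
| .75 SD | 32% / 28% | 72% / 72% | 96% / 97% |
| 1.0 SD | 48% / 53% | 93.5% / 95.5% | 100% / 100% |

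With 1,000 runs at the central values (.75 SD, r = .5), the rates were 74.6% reverse and 75.0% forward; the Monte Carlo standard error is √(.75 × .25 / 1000) = 1.4 points. At autocorrelation .6 (500 runs) they were 45.6% and 47.4%. Meeting the conditions says nothing about direction.

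**Size of the spurious share.** In standardised units under reversal, the experiment's effect on the mediator is r times its effect on ideation, and the same-day slope of ideation on the mediator is r. The apparent mediated share is therefore r × r = r²: 9% at r = .3, 25% at .5 and 49% at .7. The central simulation gave 25.3%.

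**What a lagged model adds.** Each seven-day block has six consecutive-day pairs, so there are 4 × 6 = 24 pairs per person. Both days are observed with probability .85², which leaves 85 × 24 × .85² = 1,474 pairs. For a true next-day effect, power at one-sided .004 is 87% for .10 person-SD and 25% for .05.

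If a significant forward lag were also required, the share of positive trials at the central values would be:

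| Truth | No lag required | Lag at one-sided .004 | Lag at two-sided .05 |
|---|---|---|---|
| Ideation drives hopelessness | 74.6% | 0.4% | 4.6% |
| Hopelessness drives ideation, same day only | 75.0% | 1.0% | 4.8% |

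When the effect stays within one day, the lag removes true and false findings alike. When there was some next-day carry-over, or the two ratings differed in day-to-day persistence, the forward and reverse pair did separate the directions: the lag in the true direction was flagged in about 100% of trials and the other in about 5%.

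**The case against.** The strongest reply is that the hypothesis is itself partly same-day: hopelessness is expected to matter when arousal is also raised that day, and neuroactive steroids are said to act rapidly. A concurrent model suits that hypothesis, and a rule making the lag a condition for any claim of mechanism would discard most true same-day mediators, as the second table shows. This stands. It rules out a lag veto, but it does not give the same-day model any power to show direction.

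Four stronger readings are tempting, and the documents do not support them.

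- *That the plan would declare mediation whenever ideation drives hopelessness.* The SAP says that mediation is explored where appropriate, and no rule treats a positive interval as proof of direction. The simulated rate also falls to about 8% when reversal is weak.
- *That false mediation is near certain even at modest effects.* At .5 SD and r = .5 a rate of about 82% is obtained only by leaving out the step 4 conditions and day-to-day autocorrelation. With both it is 37%.
- *That all nine mediators are equally exposed.* The same-survey argument covers hopelessness and the Brief Agitation Measure against ideation. Planning and attempts come from the daily phone screen, accelerometer and typing measures are recorded passively, and the autonomic, steroid and mRNA measures are laboratory-based. Reversal is less plausible for steroid levels.
- *That the cited evidence makes a one-day lag the correct test.* The protocol does not give the interval between time points in that report, and it also relies on its own prior-trial mediation results.

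**Conclusion.** The point holds in a limited form. Steps 2 to 4 test the mediator-outcome link only concurrently, and the step 4 conditions cannot distinguish a mediator from a consequence of ideation. For the two self-reported daily mediators, a reverse-caused symptom passes about as often as a true mediator: about 75% each at the central values, and roughly 8% to 100% across the range examined. These rates rest on assumed within-person coefficients and autocorrelation, and on applying the power-analysis alpha to step 4. The equality of the two rates depends less on those values, because the conditions treat mediator and outcome alike. The consequence is a limit on what a same-day indirect effect may be said to show, not a reason to abandon the same-day analysis.

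**What to change.** Keep the same-day model as primary. Add to SAP step 4 and Protocol 10.0, as prespecified sensitivity analyses for the daily mediators:

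1. *Forward lag-1 model:* ideation on day t on the person-centred mediator on day t−1, adjusted for ideation on day t−1.
2. *Reverse lag-1 model:* the mediator on day t on person-centred ideation on day t−1, adjusted for the mediator on day t−1.
3. *Reporting rule:* describe a same-day indirect effect as consistent with mediation, direction not established, unless the forward lag is supported and the reverse is not. State that a null lag is not evidence against mediation.

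The SAP lists four daily mediators (hopelessness, agitation, accelerometer displacement, typing instability), so against ideation this means 4 × 2 = 8 further models on data already being collected. The downside is that the pair is uninformative if effects act wholly within one day; the reporting rule allows for that.

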We define **hyperarousal** (RDoC Arousal and Regulatory Systems) as (1) self-reported agitation and overwhelm, (2) psychomotor agitation (smartphone accelerometer instability/movement^{13,14}), (3) behavioral reactivity to external stimuli (smartphone typing speed instability^{13,14}, attentional bias toward angry/fearful faces on task¹⁵), and (4) physiological hyperarousal (reduced resting parasympathetic autonomic function¹⁶, increased sympathetic and decreased parasympathetic autonomic function during an emotionally arousing task).

[figure not shown]
We define **hopelessness** as a state of despair *arising due to repeated experiences of loss or sustained threat* (RDoC Negative Valence Systems). It will be measured primarily as self-reported hopelessness using the Beck Hopelessness Scale (BHS)¹⁷, and we will measure lifetime and daily exposure to loss and threat^{18,19}.

We define **proximal suicide risk** as the presence and severity of self-injurious thoughts and behaviors as assessed dimensionally using the Adult SI Questionnaire (ASIQ)²⁰ and categorically using the Self-Injurious Thoughts and Behaviors Interview -Revised (SITBI-R). These instruments assess for passive and active SI; suicide plans; aborted, interrupted, and actual suicide attempts; and suicide death. Although non-suicidal self-injury (NSSI) is a distinct but related phenomenon, we also consider NSSI as an index of proximal risk given its predictive validity for suicide attempt²¹.

[figure not shown]
Premise for Aim 1a

Perimenstrual Hormone Withdrawal Causes Proximal Suicide Risk

In the first prospective study¹² of daily suicide risk in females with SI (K99MH109667), the PI found that proximal suicide risk peaks perimenstrually, during periods of natural hormone (E2+P4) withdrawal (Fig. 3). 38 females with past-month SI completed daily ratings on the ASIQ²⁰ across a baseline menstrual cycle. ASIQ scores peaked during the perimenstrual weeks relative to late follicular week, $\gamma=-.88$, $p<.001$ and early luteal week, $\gamma=-.56$, $p<.001$. We also observed greater odds of endorsing suicidal planning items on perimenstrual vs. non-perimenstrual days (OR=4.29, $p<.001$). 28 of 30 participants reported the highest mean SI perimenstrually. *These data support the premise that suicide risk peaks perimenstrually.*

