Sources of neuroactive steroid withdrawal: Changes in Precursor Levels. Changes in ALLO levels can be caused by both changes in the availability of steroid precursors (P4) and by changes in the expression of biosynthetic enzymes that control conversion of the precursor to ALLO. ALLO fluctuates across the menstrual cycle with changes in P4 and E2, showing lower and more stable levels in the follicular phase, increasing during the early luteal week, peaking in the midluteal phase, and falling during the perimenstrual weeks. Since P4 is a precursor, perimenstrual withdrawal from P4 generally causes corresponding withdrawal from ALLO around the onset of menses, although the trajectory and degree of this withdrawal may be influenced by many additional between- and within-person factors. For example, because E2 increases synthesis of ALLO by increasing expression of 3 α -HSDII in the brain⁵⁹, E2 changes also shape perimenstrual ALLO withdrawal.

Sources of neuroactive steroid withdrawal: Changes in central biosynthetic enzyme activity. In addition to effects of neuroactive steroids that have been synthesized from precursors in the periphery, neuroactive steroids can be directly synthesized de novo in brain⁶⁰, and ALLO’s enzymatic pathway (e.g. 5 α -RI) is expressed particularly in brain corticolimbic

regions relevant for emotion and stress responses⁶¹⁻⁶⁴. Of note, individual differences and circumstances can affect the degree to which ALLO's enzymatic pathway is expressed in the brain, and these changes in enzyme expression can be reliably measured via peripheral monocyte mRNA expression. Increases or decreases in expression of these biosynthetic enzymes (5 α -RI, 3 α -HSDII) have been shown to relate to risk for neuropsychiatric illness. Postmortem studies (from co-I [name]) reported decreased 5 α -RI mRNA expression in the PFC of depressed subjects compared with non-depressed controls⁶⁵. Suppressed ALLO levels have been found in the CSF of females with post-traumatic stress disorder (PTSD)⁶⁶ and depression⁶⁷, and elevated 5 α -DHP/ALLO ratios have been observed in the serum of those with PTSD⁶⁸, *but not in those with a history of trauma who did not develop PTSD*, suggesting a possible role of disturbed neurosteroidogenic enzyme activity in the etiology of both hyperarousal and hopelessness phenotypes.

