AIM 1: To evaluate hyperarousal and hopelessness as interacting mechanisms by which perimenstrual E2+P4 withdrawal (vs. experimental stabilization) increases proximal suicide risk. We predict that **(1a)** individuals will demonstrate greater proximal suicide risk during perimenstrual E2+P4 withdrawal (placebo) than during perimenstrual E2+P4 stabilization, an effect mediated by **(1b)** indices of hyperarousal, **(1c)** indices of hopelessness, and **(1d)** their interaction (i.e., with hopelessness predicting suicide risk only during hyperarousal).

AIM 2: To evaluate neuroactive steroid withdrawal as a mechanism by which perimenstrual E2+P4 withdrawal (vs. stabilization) increases proximal suicide risk. We expect that E2+P4 withdrawal (vs. stabilization) will induce neuroactive steroid withdrawal to some degree in all participants. However, we predict that the effect of hormone withdrawal (vs. stabilization) on proximal suicide risk at each lab will be mediated by **(2a)** degree of reduction in serum neuroactive steroid levels and **(2b)** degree of reduction in mRNA expression for neurosteroidogenic enzymes. We will also evaluate

within-person links between neuroactive steroids and all behavioral constructs; if appropriate, a multilevel mediation model will test the full model in Fig. 1.

AIM 3: To characterize GABA_{AR} gene expression plasticity across the cycle in individuals with and without perimenstrual changes in affective and suicide risk. In the HC group, we hypothesize that gene expression for $\alpha 4$ and δ subunits (GABRA4 and GABRD genes, respectively) are upregulated and $\gamma 2$ (GABRG gene) is downregulated in the midluteal (high ALLO) and perimenstrual (ALLO decline) phases compared to the midfollicular phase (low ALLO). We also hypothesize that clinical group moderates the effect of cycle phase on GABA_{AR} composition, such that the group with perimenstrual increases in affective symptoms and suicide risk shows higher slope of midluteal-to-perimenstrual change in $\alpha 4$ and δ subunits, and lower $\gamma 2$ subunit replacement of δ subunit expression than the HC group.

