2. **For laboratory visit outcomes**, we will again utilize multilevel models (with 10 labs per person—5 per condition—nested within individuals; two-level models). A two-level model will predict each repeated measures lab outcome from covariates (daily pain, illness, PRN medication use) and the interaction between (1) **experimental condition** (a dichotomous variable coded as 0 for natural hormone withdrawal condition and 1 for hormone stabilization condition) and (2) **condition phase**, a categorical (contrast) variable coded as follows: *midluteal baseline visit*, *perimenstrual experimental visit*, and the *medication withdrawal visit*. **Number of lab observations per person.** For the primary contrast between the midluteal and perimenstrual experimental phases, there are 4 observations per person—2 per condition. Based on our preliminary data from the K99 trial (identical experimental manipulation), we anticipate very minimal missing laboratory data (see grant for details) but have estimated that on average each completer participant will miss .25 visits.
3. **Hypothesized Pattern of Effects for Daily and Lab outcomes:** A significant interaction between experimental condition and condition phase is hypothesized for all twelve specified outcomes such that, in the natural withdrawal condition we expect deleterious changes from the midluteal phase to the premenstrual and menstrual phases (due to corresponding hormone withdrawal), but in the hormone stabilization condition we expect no deleterious changes (or less severe changes) from the midluteal to the premenstrual and menstrual phases (since hormone withdrawal is prevented).

Testing Associations Between Mediators and Suicide Outcomes: Aim 1 and 2 next require that we evaluate the day-to-day or week-to-week associations between single mediators (listed above) and suicide outcome variables on the same day or visit. This will be carried out in similar multilevel models as above, predicting each of the three primary suicide outcomes from person-centered values for each of the 9 mediators (listed above).

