- Aim 1 Mediation Outcomes (for Mediation by Hopelessness, Arousal). Aim 1 focuses on mediation of our experimental effects by hopelessness, hyperarousal, and their interaction. The primary hopelessness outcome will be (4) daily hopelessness on items from the Beck Hopelessness Scale (validated against full BHS in the laboratory; ICC=.32 in K99 trial). The primary arousal outcomes will be (5) daily hyperarousal as measured with the Brief Agitation Measure (validated against POMS Arousal subscale in the laboratory; ICC=.26 in K99 trial), (6) daily total smartphone accelerometer displacement reflecting overall locomotor activity (measured continuously using our BiAffect app, per reviewer recommendation; ICC=.54 in Co-I [name]'s prior study in patients with bipolar disorder), and (7) daily average typing speed instability reflecting greater reactivity to external stimuli (measured using our Biaffect App; ICC=.38 in Co-I [name]'s prior study in patients with bipolar disorder), (8) degree of RSA withdrawal during the Face Matching Task (no ICC estimate available for repeated administration; we assume a moderate ICC between .4-.6), and (9) degree of PEP shortening during the Face Matching Task (no ICC estimate available for repeated administration; we assume a moderate ICC between .4-.6).
- Aim 2 Mediation Variables (Mediation by Neurosteroids and Neurosteroidogenic Enzymes). Aim 2 focuses on mediation of our experimental effects by neuroactive steroid levels and mRNA expression for neurosteroidogenic enzymes. The primary outcomes will be (10) levels of allopregnanolone as measured using GC-MS; average ICC of .29 in former K99 mentor's prior trials with 4 measures across the cycle in naturally cycling women), (11) gene expression for 5a-RI (no ICC estimate available for repeated administration; we assume a moderate ICC between .4-.6)., and (12) gene expression for 3a-HSDII.

ANALYTIC STEPS

Specification of Steps for Analytic Plan:

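### Aim 2 hypothesises mediation by a fall in neurosteroids, but the planned mediator is the person-centered level, which cannot by itself separate falling from low once late visits enter the model

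*SAP*

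**What the plan says.** - **Hypothesis.** Protocol 3.0, Aim 2, says the effect of hormone withdrawal on risk at each lab is mediated by (2a) the "degree of reduction in serum neuroactive steroid levels" and (2b) the "degree of reduction in mRNA expression for neurosteroidogenic enzymes".
- **Variable.** SAP, Outcome Specification, lists outcome 10 as "levels of allopregnanolone as measured using GC-MS" and outcomes 11 and 12 as gene expression for the two enzymes. No change, slope or lagged score is defined.
- **Mediator-outcome step.** SAP, Analytic Steps, step 2, relates mediator and outcome on the same day or visit, "predicting each of the three primary suicide outcomes from person-centered values for each of the 9 mediators (listed above"). Protocol 10.0 has the same form: "person-centered values for each of the 9 mediators (listed above").
- **Gate and indirect effect.** Step 4 runs mediation only if the experiment affects both outcome and mediator and the person-centered variable is associated with the outcome. The indirect effect starts from condition by phase.
- **Biology.** Protocol 2.0 describes allopregnanolone as "showing lower and more stable levels in the follicular phase, increasing during the early luteal week", and reports that "ASIQ scores peaked during the perimenstrual weeks relative to late follicular week". Its Premise for Aim 3 points to change in allopregnanolone as the trigger. Its Premise for Aim 1a reports that, under active treatment in the prior trial, risk appeared later, on withdrawal from the exogenous hormones.
- **Visits.** Labs fall on days +7, +10, +14, +18 and +22. The SAP's lab model has 6 labs per person, Protocol 10.0 has 10, and both give 4 for the primary midluteal-perimenstrual contrast. Step 2 does not say which visits it uses.

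**The concern.** The hypothesis is about a fall; the planned predictor is a level. The protocol's own account separates the two: in the follicular phase allopregnanolone is low but stable, and ideation is below its perimenstrual peak.

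The difference matters at day +22. With a luteal phase of about 14 days (an assumption; the documents give no figure), placebo day +22 is about cycle day 22 - 14 = 8, so follicular: low, with the fall already over. Active day +22 comes just after the two weeks of dosing: low, with the fall recent. The level scores these visits almost alike, while the withdrawal hypothesis expects higher risk at the second.

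What is at stake is the reading of a positive result. An association between lower level and higher risk is compatible with low level as the driver and with recent decline as the driver. Neurosteroid withdrawal is the central hypothesis, and the plan contains no term that tells these apart.

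**Working it through.** **1. The plan's own figure.** The allopregnanolone row of the SAP power table reproduces. With 4 - .25 = 3.75 visits per person and ICC .29, effective N = 85 x 3.75 / (1 + 2.75 x .29) = 318.75 / 1.7975 = 177.3 (stated 177). Power for f² = .10, three predictors, one-tailed .004, is .935 (stated .93). This is power for condition by phase on allopregnanolone. The SAP gives none for the mediator-outcome or mediation step.

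**2. Which visits the SAP counts.** The supplemental table's 53 and 74 participants are matched by 5.75 visits per person (52 and 74), not by 3.75 (61 and 80). The SAP therefore uses the 4-visit count in one table and what looks like the 6-visit count in the other.

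**3. Level against fall.** Assumed relative allopregnanolone at +7/+10/+14/+18/+22:
- placebo 1, .85, .30, .10, .10 (sum 2.35)
- active 1, 1, 1, 1, .20 (sum 4.20)

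Person mean = 6.55 / 10 = .655. Placebo +22: level .10 - .655 = -.56, fall .10 - .10 = 0. Active +22: level .20 - .655 = -.46, fall 1 - .20 = .80.

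Over the 10 visits the falls are 0, .15, .55, .20, 0 (placebo) and 0, 0, 0, 0, .80 (active). Sums of squares about the mean are 1.582 (level) and .716 (fall), and the cross-product is -.641. So r = -.641 / √(1.582 x .716) = -.60 and r² = .36.

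Range of r² over the assumed profile sets:

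| Visits | r², level with fall since previous visit |
|---|---|
| 10 (protocol) | .31-.43 |
| 6 (SAP, taken as +7/+14/+22) | .53-.76 |
| 4 (primary contrast, taken as +7/+14) | .84-.91 |

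If reduction means the drop from day +7, its correlation with the level is .92-.97 in absolute value whichever visits are used.

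**4. Power.** Simulation inputs, all assumed: 90 people, the profile above, log-normal person multiplier SD .3, assay SD .15, day +7 fall set to 0, within-person regression, two-sided .004. Driver explaining 2/3/5% of within-person variance:

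| True driver, visits | Level alone | Fall alone | Fall, with level in the model |
|---|---|---|---|
| Recent fall, 10 | .32/.55/.84 | .77/.94/.998 | .38/.67/.94 |
| Recent fall, 6 | .33/.57/.82 | not used | .12/.24/.49 |
| Drop from day +7, 10 | .87/.99/1.0 | .21/.40/.69 | not used |

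In the 4-visit contrast the fall term beside the level has power of only .006-.024, close to alpha.

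**5. Does the joint model discriminate?** With 10 visits, if level alone drives risk (3% of variance), the level term is significant in 91% of trials and the fall term in 0.9%. If the recent fall drives risk, the level term is significant in about 1%. With level as the only predictor and level as the only driver (3%), the test is significant in 98% of trials. That is a correct detection of a level effect, but nothing in the plan would mark it as such.

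**The case against.** **The randomised path already tests decline.** Step 4 requires an experimental effect on the mediator, and condition by phase on allopregnanolone tests whether stabilization prevented the midluteal-to-perimenstrual change. This stands for that path. It shows that decline was prevented, not that decline rather than low level drives risk.

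**The outcome model may keep condition by phase.** Step 2 calls for models similar to those of step 1. If the phase terms stay, the two day +22 visits have separate cell means. That reduces the problem but does not remove it: within cells, level and recent fall still correlate only .61-.79 in absolute value, and the term tested is still the level.

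**Reduction is undefined.** The hypothesised pattern, change from midluteal to premenstrual and menstrual phases, fits a drop from day +7 at least as well as a visit-to-visit fall. On that reading the level is nearly the right variable, and placebo day +22 properly counts as reduced. This stands, and it is why the level should not be replaced.

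**A stronger reading to resist.** A reader might infer that level coding costs power in general and could wrongly close the gate on Aim 2. The documents do not support this. The loss needs the recent fall to be the driver and late visits to be in the model. In the 4-visit contrast it is 2-7 points, it reverses if reduction means the drop from day +7, and at about 9% of variance, close to the SAP's f² = .10, level coding has .99 power even with 10 visits and the fall as driver.

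**Conclusion.** The mismatch between hypothesis and mediator is in the text, and it limits interpretation. With late visits modelled, a significant person-centered level association cannot by itself be reported as mediation by withdrawal. Without them, low and falling are almost the same variable and cannot be separated at all.

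A reader might also infer that the trial cannot show withdrawal to be the mechanism. That goes too far: the limit applies to the mediator-outcome step as specified, and samples from all five visits per condition allow a model that does discriminate.

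The day +22 argument assumes a luteal phase of about 14 days. The numerical sizes rest on assumed allopregnanolone profiles and noise; the documents supply neither. The documents describe no cycle profile for enzyme mRNA, so for outcomes 11 and 12 only the mismatch in wording is established. This is a should-fix point on analysis and reporting, not a flaw in the design.

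**What to change.** 1. State what reduction means in Aims 2a and 2b: drop from day +7, or fall since the previous visit.
2. Keep the person-centered level as the planned mediator and gate.
3. For outcomes 10-12, add a pre-specified model with two terms: the person-centered level, and the fall since the previous visit within the same condition (previous value minus current value). Use all five visits per condition.
4. Allow step 4 to be run for the fall as well, and attribute mediation to withdrawal only if the fall term is supported. Otherwise report an association with level.
5. Reconcile the SAP's 6 labs with the protocol's 10, and name the visits that enter steps 2 and 4. The two terms separate poorly with 6 visits and not at all in the 4-visit contrast.

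**Cost.** SAP wording and a variable derived from samples already planned at every visit. A difference score carries assay noise from two samples and has no value at day +7. Power for the fall in the joint model is modest with 10 visits (about .38/.67/.94 at 2/3/5%). With 6 visits it is lower than that of the level test alone, so an unsupported fall term should be reported as inconclusive, not as evidence against withdrawal.
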